8.3. Kidney Biopsy

Study participants will undergo surveillance biopsies as standard of care between 3 and 7 months after transplantation and approximately one year after transplantation. Research specimens will be collected during these procedures and digital images will be sent to the central pathologist for scoring. The biopsy obtained 3-7 months after transplantation will be used to determine study eligibility and local read will be confirmed by central pathologist. The one-year biopsy will fall 7 months after study group assignment and will be used to assess the efficacy endpoint. The one-year biopsy and all for-cause biopsies will be reviewed by the central pathologist.

Additionally, a protocol kidney biopsy will be performed 2 weeks after polyTreg infusion (Group 2). This biopsy is for research purposes only and will be used for mechanistic assays and to confirm eligibility for mTOR conversion. This biopsy will be reviewed by the central pathologist.

9. Known and Potential Risks and Benefits to Participants

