15.3.2.4 Secondary Efficacy Endpoints

Table 8 describes secondary efficacy endpoints and their corresponding parameters to be estimated in the study.

Efficacy endpoints will be listed or summarized, as appropriate, using standard descriptive statistics for continuous and categorical data, including confidence intervals. All secondary endpoints will be descriptive in nature due to the small sample size.

Table 8. Analyses of Secondary Efficacy Endpoints		
SECONDARY ENDPOINT	DESCRIPTIVE PARAMETER	ANALYSIS SAMPLE*
Number of subjects who exhibit a relative decrease of 25% or more inflammation on kidney biopsy 7 months after study group allocation compared to baseline	Proportion with exact binomial 95% confidence limits	mITT1
Number of subjects who exhibit a relative decrease of 25% or more inflammation on kidney biopsy 2 weeks after Treg infusion compared to baseline	Proportion with exact binomial 95% confidence limits	mITT2
Number of subjects who exhibit a relative decrease of 50% or more inflammation on kidney biopsy 2 weeks after Treg infusion compared to baseline	Proportion with exact binomial 95% confidence limits	mITT2

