#### 4. ANALYSIS SAMPLES

**Modified Intent-to-Treat Sample 1 (mITT1)** – The mITT1 sample consists of all subjects allocated to the CNI-based treatment regimen or received polyTregs while on study.

**Modified intent-to-Treat Sample 2 (mITT2)** – The mITT2 sample consists of all subjects who received polyTregs (Group 2).

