### **8.2.1. Endpoints**

**Variable:** Secondary incidence endpoints including:

Endpoint	Time Frame
polyTreg infusion reactions	405 days post-group allocation
Culture-proven and clinically diagnosed infections	405 days post-group allocation

Acute rejection using Banff grading	405 days post-group allocation
BK viremia after polyTregs infusion	405 days post-group allocation
CMV reactivation after polyTregs infusion	405 days post-group allocation
>10% decrease in eGFR compared to baseline	405 days post-group allocation
Acute rejection after converting to mTOR therapy after polyTregs infusion	69 days post-group allocation to 405 days post-group allocation
Proportion of participants exhibiting $\geq 25\%$ decrease of inflammation between baseline kidney biopsy and the week 2 kidney biopsy	Baseline biopsy to Week 2 kidney biopsy
Proportion of participants exhibiting $\geq 50\%$ decrease of inflammation between baseline kidney biopsy and the week 2 kidney biopsy	Baseline biopsy to Week 2 kidney biopsy
Proportion of participants exhibiting $\geq 25\%$ decrease of inflammation between baseline kidney biopsy and the month 6 kidney biopsy	Baseline biopsy to 6 month kidney biopsy (for polyTregs infusion group). Baseline biopsy to 7 months post-group allocation (for maintenance therapy group).

**Analysis:** For each of the above incidence endpoints, the proportion of participants with events will be reported by treatment group and compared using Fisher's Exact test or a Cochran-Mantel-Haenszel test.

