**Population-level summary:**

- **polyTreg infusion reactions - mITT2**
- **Acute rejection using Banff grading** – mITT1, subset to participants that have available Banff lab data
- **Acute rejection after converting to mTOR therapy after polyTregs infusion** - mITT2
- **Proportion of participants exhibiting  $\geq 25\%$  decrease of inflammation between baseline kidney biopsy and the week 2 kidney biopsy** – mITT1, subset to participants with available LCA data from week 2 visit
- **Proportion of participants exhibiting  $\geq 50\%$  decrease of inflammation between baseline kidney biopsy and the week 2 kidney biopsy** – mITT1, subset to participants with available LCA data from week 2 visit
- **Proportion of participants exhibiting  $\geq 25\%$  decrease of inflammation between baseline kidney biopsy and the month 6 kidney biopsy** – mITT1, subset to participants with available LCA data from 6 month visit
- All other endpoints will use the mITT1 sample

**Variable:** Secondary timing endpoints including:

Endpoint	Time Frame
polyTreg infusion reactions	405 days post-group allocation
Culture-proven and clinically diagnosed infections	405 days post-group allocation
Acute rejection using Banff grading	405 days post-group allocation
BK viremia after polyTregs infusion	405 days post-group allocation
CMV reactivation after polyTregs infusion	405 days post-group allocation
>10% decrease in eGFR compared to baseline	405 days post-group allocation
Acute rejection after converting to mTOR therapy after polyTregs infusion	69 days post-group allocation to 405 days post-group allocation

**Analysis:** For each of the above timing endpoints, the mean or median time of event (study days since start of treatment) will be reported by treatment group and compared using ANOVA or the Kruskal-Wallis test (or t-test for comparison of Groups 1 and 2).

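### SAP 8.2.1 orders between-group tests of week-2 response and infusion reactions, but Group 1 has no week-2 biopsy and no infusion, so no valid comparison exists

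*SAP*

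**What the plan says.** SAP 8.2.1 puts all secondary incidence endpoints in one table. The rows include polyTreg infusion reactions and decreases of at least 25% and at least 50% between the baseline and week-2 biopsies. One instruction then covers the whole table: "For each of the above incidence endpoints", it says, "the proportion of participants with events will be reported by treatment group and compared using Fisher's Exact test or a Cochran-Mantel-Haenszel test". No row is excepted. Infusion reactions appear again in the timing list, to be compared by ANOVA, Kruskal-Wallis or t-test, and in the severity list, to be compared by Fisher or Cochran-Mantel-Haenszel (CMH).

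The populations follow each list. The SAP gives "polyTreg infusion reactions - mITT2" for incidence and uses mITT2 again for timing and severity. SAP section 4 limits mITT2 to polyTreg recipients. Each week-2 response is set in "mITT1, subset to participants with available LCA data from week 2 visit".

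The protocol plans something different:

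- Table 8 places both week-2 responses in mITT2, as a proportion with exact limits.
- Table 7 does the same for infusion-reaction incidence, and gives severity as descriptive CTCAE categories.
- Section 15.3.2.4 states: "All secondary endpoints will be descriptive in nature due to the small sample size".
- Section 15.5 is more explicit: because the sample is small, secondary endpoints are to be described and not tested between groups.

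**The concern.** A two-group test needs observations in two groups. The general instruction in SAP 8.2.1 is applied to endpoints that can be observed only in people who were infused. The 25% week-2 response is the whole content of the secondary efficacy objective (protocol 1.5) and the first secondary efficacy endpoint named in protocol 3.5. As the SAP stands, the only inference specified for it is a comparison with an empty group.

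Two things are at stake. An output table could show a p-value that carries no information and might be read as showing no difference. And the statistic that does carry information here, an interval around the Group 2 proportion, is not in the SAP: 8.2.1 specifies none, and the conventions in SAP section 7 ask only for counts and percentages.

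**Working it through.** The documents give no figure for these endpoints to reproduce. The power table in protocol 15.5 concerns the primary efficacy endpoint only.

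**Step 1. Who can contribute data?**

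- *Week-2 biopsy.* Protocol 8.3: "a protocol kidney biopsy will be performed 2 weeks after polyTreg infusion (Group 2"). The study design row in SAP section 3 likewise gives the day-14 biopsy to infused participants. The Group 1 schedule (protocol Appendix 2) marks biopsy material at screening, Day 223 and clinically indicated biopsies. Group 1's parallel Visit 2 (Day 55) has no biopsy.
- *Infusion.* Group 1 stays on standard CNI maintenance without Tregs (SAP section 3, treatment description).
- *Other possible comparators.* People assigned to polyTregs but not infused move to Group 1 (SAP 6.2), so they have no post-infusion biopsy. The one darTreg participant is excluded from efficacy analyses (SAP 8.1) and is outside mITT2. A for-cause biopsy in Group 1 is not the week-2 biopsy.

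Group 1 therefore has n = 0 for the two week-2 responses and for incidence, timing and severity of infusion reactions.

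**Step 2. What do the ordered tests return?** Take Group 2 as the planned 7, with k events, and Group 1 as 0.

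- *Fisher.* With row totals 0 and 7 and column totals k and 7 − k, only one table is possible. Its probability is C(0,0) × C(7,k) / C(7,k) = 1. So p = 1 for every k from 0 to 7, and the odds ratio is undefined.
- *CMH.* The variance is n1 × n2 × m1 × m2 / (N² × (N − 1)). With k = 3 this is 0 × 7 × 3 × 4 / (49 × 6) = 0. Observed minus expected is also 0, so the statistic is 0/0.
- *ANOVA, Kruskal-Wallis or t-test for timing.* With one group the between-group degrees of freedom are 1 − 1 = 0, so there is no statistic.

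**Step 3. What would the protocol's summary give?** Exact (Clopper-Pearson) 95% limits at n = 7. The documents report no event counts, so every possible count is shown.

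| Count | Lower | Upper |
|---|---|---|
| 0/7 | 0% | 41.0% |
| 1/7 | 0.4% | 57.9% |
| 2/7 | 3.7% | 71.0% |
| 3/7 | 9.9% | 81.6% |
| 4/7 | 18.4% | 90.1% |
| 5/7 | 29.0% | 96.3% |
| 6/7 | 42.1% | 99.6% |
| 7/7 | 59.0% | 100% |

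The two end rows can be checked by hand: 0.025^(1/7) = 0.590, so 7/7 has lower limit 59.0%, and 0/7 has upper limit 1 − 0.590 = 41.0%.

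**Step 4. Is the change declared?** SAP section 10 records a change of population for the two week-2 responses. It mentions neither the move from description to testing nor the missing exact limits.

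**The case against.** The best defence is that little would go wrong in practice. The SAP asks for two things, a proportion by group and a comparison, and only the second is empty. Software would print p = 1 or a missing value, and a competent analyst would report Group 2 alone. The move from mITT2 to mITT1 is close to nominal, because restricting mITT1 to those with week-2 LCA data leaves infused participants with a reading, and section 10 declares it. SAP 7.1.4 calls the analysis primarily descriptive. Protocol 3.3.1 itself lists infusion reactions under wording about comparison with Group 1. No decision rule rests on these endpoints.

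Most of this stands and limits the size of the point. It does not remove the instruction. SAP 7.1.4 concerns multiplicity adjustment and does not cancel the tests ordered in 8.2.1. Protocol Table 7 settles the wording of 3.3.1 by placing infusion reactions in mITT2.

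A reader might infer three stronger things that the documents do not support:

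- *That Group 1 would be entered as non-responders, giving a spurious treatment effect.* The SAP's own populations rule this out: week-2 response requires week-2 LCA data, and infusion reactions are set in mITT2.
- *That the week-2 endpoint has no valid analysis at all.* The Group 2 proportion is still produced.
- *That the exact limits were deliberately dropped.* The SAP is silent on them and section 10 lists no such decision. They were not carried over.

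**Conclusion.** The point holds in a limited form. For two week-2 response endpoints and three aspects of infusion reactions, the SAP orders a between-group test whose comparator is n = 0. This follows from the biopsy schedule, the treatment description and the SAP's population definitions, and does not depend on any assumed event rate. The SAP also departs, without recording it, from the protocol's rule that secondary endpoints are described and not tested, and it omits the precision statement that the protocol specifies.

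The consequence is an uninformative p-value and a missing interval, not a biased result. The interval widths assume all 7 planned Group 2 participants contribute; with missing biopsies the denominator would be smaller. The primary endpoints are untouched. So is the empty-comparator problem for the 25% response at month 6/7, where both groups have a biopsy. Acute rejection after mTOR conversion is a separate matter, since protocol Table 7 defines a contrast within Group 2.

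**What to change.** In SAP 8.2.1:

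- *25% and 50% week-2 responses:* report Group 2 only, meaning mITT2 participants with week-2 LCA data, and state how many are missing. Give the proportion with exact binomial 95% limits and no between-group test.
- *Infusion reactions (already mITT2, so no change of population):* give incidence as a proportion with exact 95% limits, timing by descriptive statistics and severity by CTCAE category. Run no between-group test for any of the three.
- *SAP section 10:* revise the entry for the week-2 responses to match, and state explicitly how these endpoints are analysed relative to the protocol.

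The cost is SAP wording and the matching table shells. No new data, visits or participants are needed.

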**Population-level summary:**

- **polyTreg infusion reactions - mITT2**
- **Acute rejection using Banff grading** – mITT1, subset to participants that have available Banff lab data
- **Acute rejection after converting to mTOR therapy after polyTregs infusion** - mITT2
- **Proportion of participants exhibiting  $\geq 25\%$  decrease of inflammation between baseline kidney biopsy and the week 2 kidney biopsy** – mITT1, subset to participants with available LCA data from week 2 visit
- **Proportion of participants exhibiting  $\geq 50\%$  decrease of inflammation between baseline kidney biopsy and the week 2 kidney biopsy** – mITT1, subset to participants with available LCA data from week 2 visit
- **Proportion of participants exhibiting  $\geq 25\%$  decrease of inflammation between baseline kidney biopsy and the month 6 kidney biopsy** – mITT1, subset to participants with available LCA data from 6 month visit
- All other endpoints will use the mITT1 sample

**Variable:** Secondary timing endpoints including:

Endpoint	Time Frame
polyTreg infusion reactions	405 days post-group allocation
Culture-proven and clinically diagnosed infections	405 days post-group allocation
Acute rejection using Banff grading	405 days post-group allocation
BK viremia after polyTregs infusion	405 days post-group allocation
CMV reactivation after polyTregs infusion	405 days post-group allocation
>10% decrease in eGFR compared to baseline	405 days post-group allocation
Acute rejection after converting to mTOR therapy after polyTregs infusion	69 days post-group allocation to 405 days post-group allocation

**Analysis:** For each of the above timing endpoints, the mean or median time of event (study days since start of treatment) will be reported by treatment group and compared using ANOVA or the Kruskal-Wallis test (or t-test for comparison of Groups 1 and 2).

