10.2. Study Eligibility and Study Group Allocation

Subjects will have a renal allograft biopsy performed 5 months (± 8 weeks) after transplantation. Biopsy results will be an integral part of screening for study eligibility and will be confirmed by the central pathologist prior to enrollment. During the screening period the study personnel will review the subject's medical record for previous and current medical history, demographic information (age, gender, and race), medications, and laboratory test results. Additional laboratory tests, such as a pregnancy test (if applicable), will be performed at the transplant center for screening purposes. Blood, urine and tissue will be collected for central laboratory analysis.

Eligible patients will be assigned according to the allocation scheme (Section 3.7) to 2 groups: group 1 CNI maintenance; group 2 infusion of $550 \pm 450 \times 10^6$ polyTregs. The day of study group assignment is designated day 0 on the Schedule of Events (Appendix 2 and 3).

10.3. Specific Visits for Group 2

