10.6. Visit Windows

Study visits should take place within the time limits specified below (Table 2). The designated visit windows for each scheduled visit are also indicated on the Schedules of Events.

Table 2. Visit Windows	
Study Visit	Visit Window
Study Eligibility Biopsy	5 months \pm 8 weeks
Study Eligibility/ Study Group Allocation	\leq 2 weeks after qualifying biopsy
Group 1 Only	
Day 41/ Visit T0-G1	\pm 3 days
Day 48/ Visit 1	\pm 5 days
Day 55/ Visit 2	
Day 69/ Visit 3	
Day 125/ Visit 4	
Day 223/ Visit 5	\pm 14 days
Day 405/ Visit 6	
Group 2	
PBMC Collection Visit T-16	Dictated by infusion date and manufacturing timeline.
Treg Infusion Day / Visit T0	Infusion can occur any time up to and including day 62 after central pathology confirmation.
Visit T1 / Day 1	\pm 1 hour (Group 2)
Visit 1 / Day 7	\pm 1 day
Visit 2 / Day 14	\pm 3 days
Visit 3 / Day 28	
Visit 4 / Day 84	
Visit 5 / Day 182	\pm 14 days
Visit 6 / Day 364	\pm 14 days

11. Mechanistic Assays

The goal of the mechanistic studies in this trial is to evaluate the impact of polyTregs on the immunological profiles of kidney transplant recipients. We will accomplish this by determining: 1) impact of Treg infusion on the numbers of circulating and graft-infiltrating Tregs; 2) impact of Treg infusion on the inflammation in the graft; 3) impact of Treg infusion on the peripheral blood biomarkers of rejection and graft injury.

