15.3.2. Endpoint Assessments

15.3.2.1 Primary and Secondary Safety Endpoints

Table 7. Analyses of Safety Endpoints describes the safety endpoints and their corresponding parameters to be estimated in the study. Safety endpoints will be listed or summarized, as appropriate, using standard descriptive statistics for continuous and categorical data.

Table 7. Analyses of Safety Endpoints

ENDPOINT	DESCRIPTIVE PARAMETER	ANALYSIS POPULATION
Primary Endpoint		
Incidence of severe acute rejection or antibody mediated rejection in subjects receiving polyTregs in comparison with CNI-based maintenance IS therapy.	Proportion with exact binomial 95% confidence limits	miITT1
Incidence of severe infection in subjects receiving polyTregs in comparison with CNI-based maintenance IS therapy.	Proportion with exact binomial 95% confidence limits	miITT1
Secondary Endpoints – Treg safety		
Incidence of polyTregs infusion reactions (episodes of fever, bronchospasm, hypoxia, cytokine release syndrome, or infusion site reaction)	Proportion with exact binomial 95% confidence limits	miITT2
Severity of polyTregs infusion reactions	Descriptive CTCAE categories	miITT2
Incidence of culture-proven and clinically diagnosed infections	Proportion with exact binomial 95% confidence limits	miITT1
Severity of culture-proven and clinically diagnosed infections	Descriptive CTCAE categories	miITT2
Incidence of severe infection in subjects receiving polyTregs in comparison with CNI-based maintenance IS therapy.	Proportion with exact binomial 95% confidence limits	miITT1
Timing of acute rejection	Mean time to rejection and standard deviation	miITT1
Incidence of acute rejection	Proportion with exact binomial 95% confidence limits	miITT1
Severity of acute rejection	Descriptive Banff criteria	miITT1
Incidence of CMV reactivation	Proportion with exact binomial 95% confidence limits	miITT1
Incidence of BK viremia	Proportion with exact binomial 95% confidence limits	miITT1
Incidence of >10% decrease in eGFR from baseline	Proportion with exact binomial 95% confidence limits	miITT1
Secondary Endpoints – mTOR therapy		
Incidence of acute rejection	Proportion with exact binomial 95% confidence limits	miITT2 (Treg mTOR vs Treg no mTOR)

15.3.2.2 *Supportive Analyses of the Primary Safety Endpoints*

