Treatment Description	
Subjects will be on maintenance immunosuppression therapy using CNI + MMF/MPA with or without steroids at the time of study entry.
 
Eligible participants will be randomized to receive:
 
 
1. Standard CNI maintenance IS (no Tregs)
 
2. <math>550 \pm 450 \times 10^6</math> polyTregs
 
 
After receiving at least <math>300 \times 10^6</math> polyTregs infusion, eligible participants will start mTOR inhibitor.

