### **6.2. Randomization**

Participants will be assigned to the treatment groups in an unblinded fashion using a variation of the Pocock and Simon adaptive randomization strategy. A web-based randomization system will be used in order to minimize the possibility of bias entering into those assignments and to maintain approximate equality in the group sizes. The initial treatment allocation will weight each treatment equally. In subsequent allocations, the less-populated arm will be weighted more in order to restore the balance between the groups. If a recipient is assigned to polyTreg and the recipient does not receive the intended polyTreg infusion, that recipient will be re-assigned to Group 1. The allocation schedule algorithm/scheme will not incorporate stratification variables.

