### **8.1.2. Primary Analysis of the Primary Endpoint**

The ANOVA method or Kruskal-Wallis test (or t-test for comparison of Groups 1 and 2) will be used to compare treatment groups on the mean or median percent change in inflammation at 7 months post-group allocation, relative to baseline biopsy. This method will be run on the mITT1 population, subset to participants that have available LCA data from the 7 month visit post-group allocation.

The Fisher's Exact or Cochran-Mantel-Haenszel tests will be used to compare the treatment groups on the incidence of severe acute cell-mediated rejection and/or acute antibody mediated rejection. This method will be run on the mITT1 population, subset to participants that have available Banff data.

The ANOVA method or Kruskal-Wallis test (or t-test for comparison of Groups 1 and 2) will be used to compare treatment groups on the mean or median time of event of severe acute cell-mediated rejection and/or acute antibody mediated rejection. This method will be run on the mITT1 population, subset to participants that have available Banff data.

The Fisher's Exact or Cochran-Mantel-Haenszel tests method will be used to compare the treatment groups on the incidence of severe infection. This method will be run on the mITT1 population.

The ANOVA method or Kruskal-Wallis test (or t-test for comparison of Groups 1 and 2) will be used to compare treatment groups on the mean or median time of event of severe infection. This method will be run on the mITT1 population.

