## **9. SAFETY EVALUATION**

### **9.1. Overview of Safety Analysis Methods**

General safety analyses will be carried out using the mITT1 population defined in Section 4 (with the addition of the one subject who received darTregs), unless otherwise noted. Missing safety information will not be imputed. These analyses will not be stratified by site.

Safety will be analyzed in each treatment group through the reporting of AEs, vital signs, and changes in routine laboratory measures.

Listings will be prepared, if needed to fulfill regulatory reporting obligations, for all safety measurements. All listings will be sorted in order of subject identifier and time point of assessment (e.g., visit and/or time).

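### Event timing is tested on the mean or median event day of participants who had an event, with no censoring rule and a time origin that is unstated (SAP 8.1.2) or undefined for Group 1 (SAP 8.2.1)

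*SAP*

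**What the plan says.** SAP 8.2.1 lists seven secondary timing endpoints. For each, the "median time of event (study days since start of treatment) will be reported by treatment group and compared using ANOVA or the Kruskal-Wallis test"; the mean is the alternative summary, and a t-test is the option for Group 1 against Group 2. The time-frame column beside these endpoints counts days from group allocation.

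SAP 8.1.2 uses the same methods for both primary safety endpoints. For infection, for example, the aim is to "compare treatment groups on the mean or median time of event of severe infection". No origin is named there.

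Neither document gives a censoring rule, a time-to-event method, or a value for participants with no event. SAP 9.1 says only: "Missing safety information will not be imputed".

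On the origin, the SAP treatment description states: "Subjects will be on maintenance immunosuppression therapy using CNI + MMF/MPA with or without steroids at the time of study entry". Under SAP 6.2, if a polyTreg assignee is not infused, "that recipient will be re-assigned to Group 1". Protocol 10.2 offers one possible anchor: "The day of study group assignment is designated day 0 on the Schedule of Events". Protocol Table 2 offers another for Group 1: "Day 41/ Visit T0-G1".

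The protocol planned less. Table 7 gives one timing parameter, for acute rejection: "Mean time to rejection and standard deviation". Protocol 15.5 says that secondary endpoints will be described and not compared statistically between groups. SAP section 10, which lists changes from the protocol, does not mention the move to testing.

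**The concern.** Timing is part of both primary safety endpoints and of the mTOR safety endpoint, so these results will be read. Two things go wrong.

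First, an event day exists only for someone who had an event. The SAP does not say that the comparison is restricted to those participants, but without a rule for the others no other reading can be carried out. The test then conditions on the outcome. An arm with many events and an arm with few can have similar mean event days, and a participant who stays event-free for a year contributes nothing.

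Second, in 8.2.1 the clock starts at start of treatment. Group 2 has an infusion day. Group 1 continues drugs it was already taking, and participants moved into Group 1 after a failed infusion have no start either. A programmer must pick a date. The obvious choices, allocation for Group 1 and infusion for Group 2, put the arms on different clocks.

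**Working it through.** **Plan's own figure.** The documents give no figure for timing. Their only power figures are in protocol Table 11 and concern the primary efficacy endpoint. The quoted cell (difference 30, SD 15, 7 per arm, two-sided 0.05) is 92.9%, and a two-sample t-test with 12 degrees of freedom reproduces it.

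**Inputs.** 7 per arm (protocol 15.5); follow-up to day 405 from allocation, or day 364 from infusion (protocol Table 2). Event risks are assumptions, because no planning rate is given. The only background figure is early acute rejection below 15% (protocol 2.1.1).

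**1. Gap between the clocks.** Matched visits in protocol Table 2:
- Visit 2: Day 55 in Group 1, Day 14 in Group 2; 55 − 14 = 41
- Visit 3: 69 − 28 = 41
- Visit 6: 405 − 364 = 41

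The gap is nominal, because the infusion date varies.

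**2. Effect of mixed clocks when risk is equal.** Simulation of 20,000 trials, constant hazard over 364 days after T0, with 41 days added to Group 1 event days. Group 2 has the earlier mean, among trials with events in both arms:
- 15% risk: about 61%
- 30% risk: about 64 to 65%
- 60% risk: about 71%

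With a common clock the figure is 50% at each risk. The t-test falsely rejects in about 6% to 8% of computable trials, against about 5.5% to 6% with a common clock.

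**3. Whether the t-test can be computed at all.** It needs at least one event per arm and three in total. With q = 1 − (1 − p)^7 and r = 7p(1 − p)^6, the chance is q² − r²:
- p = 5%: 0.0910 − 0.0662 = 0.025
- p = 10%: 0.2722 − 0.1384 = 0.134
- p = 15%: 0.4616 − 0.1568 = 0.305
- p = 30%: 0.8421 − 0.0610 = 0.781

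**4. Whether event day reflects risk.** Under a constant hazard over T = 405 days, the mean event day given an event is T × (1/a − (1 − p)/p), with a = −ln(1 − p).
- p = 60%: a = 0.9163; 405 × (1.0914 − 0.6667) = 172.0
- p = 30%: a = 0.3567; 405 × (2.8037 − 2.3333) = 190.5

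A doubling of incidence moves the mean by 18.5 days. In simulation the t-test rejects in about 6% of computable trials, barely above its nominal level. The lower-risk arm shows the earlier mean in about 43% of trials with events in both arms, much of which is small-sample noise. A log-rank test on the same data has about 20% power, so a better method does not make the trial informative on this question.

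**The case against.** The case for leaving the plan alone has real weight. SAP 7.1.4 calls the analysis primarily descriptive. Incidence is compared separately (SAP 8.1.2 and 8.2.1), and SAP 9.3 and 9.4 plan listings of all adverse events and serious adverse events, so event dates should be recoverable. The excess false rejection is small. The 60% against 30% scenario is an assumption and hardly suits Banff 2A rejection or Grade 3 infection. Kaplan-Meier curves with 7 per arm and few events add little. All of that stands, and it limits the consequence. It does not make the specified tests meaningful, and a reported mean or median depends on the origin whether or not a p-value is attached. Protocol 15.3.3 allows simple tests in descriptive tables that include adverse events, but it does not mention event timing.

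Three stronger readings are tempting and are not supported:
- A reader might infer that the primary safety endpoints are counted from an origin that Group 1 lacks. That wording is in 8.2.1 only; in 8.1.2 the origin is simply not stated.
- A reader might infer that the mTOR time frame, day 69 to day 405, drops rejections in participants who convert before day 69. Those days are printed Group 1 visit labels (protocol Table 2 and Appendix 2: Visits 3 and 6), and SAP 7.1.2 generally includes data whatever the assessment date. The frame is probably nominal, and no loss of events is established.
- A reader might infer that infusion-reaction timing is affected too. It uses mITT2 only, so the Group 1 origin does not arise.

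**Conclusion.** The concern holds for the between-arm timing results. The tests in SAP 8.1.2 and 8.2.1 condition on having an event and cannot tell risk from timing. For the secondary endpoints they also depart from protocol 15.5 and Table 7 without being listed in SAP section 10. The origin in 8.2.1 is undefined for Group 1 and for reassigned participants, and it conflicts with the time frames beside it.

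The main harm from mixed clocks is direction: Group 2 would look earlier in roughly 61% to 71% of trials in which both arms have events, instead of 50%. This rests on assumed risks of 15% to 60%, a constant hazard and a fixed 41-day offset. The SAP does not say that the clocks will be mixed; it leaves that possible. At risks of 10% to 15% the t-test could be computed in only about 13% to 30% of trials. Safety conclusions from incidence and listings are untouched. Severity: minor to should-fix.

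**What to change.** 1. Delete the between-group ANOVA, Kruskal-Wallis and t-tests of event days in SAP 8.1.2 and 8.2.1.
2. State one matched origin for both arms. Infusion (T0) in Group 2 and T0-G1 (Day 41) in Group 1 follows the protocol's parallel visits. List earlier events, and all events in reassigned participants, separately by assigned group, so that none is lost and events that prevented infusion stay visible.
3. Show Kaplan-Meier or cumulative incidence by arm with all participants at risk, censored at last follow-up, next to event-day listings and with no claim of power.
4. For the mTOR endpoint, say that days 69 and 405 are nominal visit labels and that post-conversion events count from the actual everolimus start.
5. Reconcile whether Group 1 is a comparator for that endpoint. Protocol 3.3.2 and SAP section 3 include it; protocol Table 7 and SAP 8.2.1 use mITT2 only.

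The cost is SAP wording and standard programming, using dates already collected (allocation, infusion, event, last visit, concomitant medication). The one loss is that event timing will have no p-value.
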